14.3 Analysis of Secondary and Exploratory Objectives

Response rate will be estimated for all patients with corresponding 95% confidence intervals. Progression-free survival and overall survival times will be displayed using Kaplan-Meier curves with median survival times and confidence intervals. Adverse events will be summarized in incidence tables by type and grade severity for all patients and presented by type of treatment received. For exploratory objectives, the frequency of types of actionable mutations and previous treatment history will be summarized and demographic characteristics presented. Logistic models will be constructed for each type of mutation (yes/no) to preliminarily explore associations with clinical and demographic characteristics. For quality of life and patient satisfaction outcomes, changes over time will be assessed using a repeated measures ANOVA, with any between time associations utilizing Tukey adjustment for post-hoc comparisons. Transformations and/or non-parametric approaches will be considered for any outcomes violating parametric assumptions.

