2.2 Secondary Objectives

- 2.2.1 To estimate patient response rate on off-label treatments for actionable mutations based on NGS results.
- 2.2.2 To estimate overall survival (OS) for patients treated with off-label treatments for actionable mutations based on NGS results.
- 2.2.3 To describe the safety of using off-label or other experimental treatments for patients with actionable mutations based on NGS results.

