5.2 Secondary Outcomes

- 5.2.1 Overall survival (OS), defined as the duration of time from the start of treatment to date of death or date of last contact; those lost to follow-up will be censored.
- 5.2.2 Investigational Agent Safety To determine incidence of adverse events (AEs), serious adverse events (SAEs), and any laboratory abnormalities of each investigational agent tested.
- 5.2.3 To measure response rate of treatment based on a simplified selection methodology using the NGS results.

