	Pre-Study ^a	Cycle 2, Day 1	Day 1; every even cycle (after cycle 2)	End of Treatment ±7 days	Follow up for Safety (30+ days after last treatment) required only if pt has treatment related AEs at end of treatment visit
Informed Consent	X				
Demographics	X				
Medical History	X				
Concurrent Meds	X				
Physical Exam	X	X	X	X	X
Vital Signs	X	X	X	X	X
Performance Status	X	X	X	X	X
Bone Marrow Biopsy ^h	X	X	X	X	
Imaging ^d	X	X	X ^f	X	
CBC w/diff, platelets ^e	X	X	X	X	X
Serum Chemistry ^b	X	X	X	X	X
B-HCG ^c	X				
Dose Adjustment Form		X	X		
Adverse Event Evaluation		X	X	X	X
Survival Status/Telephone Follow up ^g					X
PROMIS 29	X	X		X	
Satisfaction with Medical Decision Scale	X	X		X	
Patient Reported Outcome- Demographics/Health Literacy	X				

^a Pre-study requirements listed in table must be completed **within** 30 days prior to registration. Imaging demonstrating disease progression should be completed within 60 days of registration. Imaging should be repeated if the scan occurred more than 30 days prior to treatment initiation..

^b Albumin, alkaline phosphatase, total bilirubin, bicarbonate, BUN, calcium, chloride, creatinine, glucose, potassium, total protein, SGOT[AST], SGPT[ALT], sodium.

^c Serum pregnancy test within 10 days of Pre-study visit (women of childbearing potential only).

^d Imaging will be performed as part of SOC for solid tumors every other cycle, however due to patients on different drug treatment regimen, this may occur at 6 weeks ±2 weeks, 8 weeks ± 2 weeks or 12 weeks ± 2 weeks. Not required for leukemias. As clinically indicated in Multiple myeloma.

^e Labs will be performed in accordance with the recommendations of the prescribing instructions for the drug that is utilized

^f If treatment is discontinued for reasons other than progression, imaging will be performed on the same schedule as was utilized while patient was receiving treatment until progression.

^g Survival and information related to cancer treatment received after the study and disease status is monitored bimonthly via telephone contact or EMR review after treatment termination. Medical record review will be performed to coincide with the bimonthly telephone call to obtain information regarding evidence and of relapse (as documented on CT, PET, biopsy, etc).

^h If clinically indicated bone marrow biopsy will be repeated to evaluate response to therapy.

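### Section 14.3 tabulates adverse events by treatment received as incidence without time at risk, although time on drug will differ between agents

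*Combined protocol and SAP*

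**What the plan says.** Safety appears at three levels of the combined protocol and SAP.

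- **Objective (2.2.3):** "To describe the safety of using off-label or other experimental treatments for patients with actionable mutations based on NGS results". It is descriptive.
- **Outcome (5.2.2):** "To determine incidence of adverse events (AEs), serious adverse events (SAEs), and any laboratory abnormalities of each investigational agent tested". The unit of reporting is the agent.
- **Analysis (14.3):** "Adverse events will be summarized in incidence tables by type and grade severity for all patients and presented by type of treatment received". No rate per unit of time, time-to-event method, exposure summary or fixed window accompanies this sentence.

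Three other sections fix who is at risk and for how long. Section 8.1.1 counts every patient as evaluable for toxicity from first treatment. Section 6.3 allows treatment for the number of cycles on the drug's label, or until progression, intercurrent illness, an unacceptable adverse event, withdrawal or an investigator's judgement. Section 6.4 requires adverse event follow-up for at least 30 days after the last dose.

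**The concern.** When patients are observed for different lengths of time, the share with at least one event depends on the event rate and on the time each patient was at risk. Here the agents are assigned by mutation and report order across many tumour types, and each has its own label. Nothing in the plan equalises time on drug between them.

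The distortion runs in an awkward direction. An agent that holds off progression keeps its patients on treatment longer and so accumulates more patients with events. In a table of incidence by treatment it can look more toxic than an agent on which patients progress quickly, even if the two have the same event rate per month. What is at stake is how the per-agent tables required by 5.2.2 are read.

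**Working it through.** **Inputs.** The documents state no adverse event rate, no expected time on drug and no number of patients per agent, so there is no figure of the plan's own to reproduce. The 30-day tail is from 6.4, taken as one month. The following are assumptions for illustration:

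- a constant hazard *h* of first event, equal for both drugs, at 0.05, 0.10 or 0.20 per month;
- exponential time on drug, independent of the event process, with a median of 2 or 6 months.

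**Step 1: crude incidence.** With mean time on drug *m* = median / ln 2 and a one-month tail,

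incidence = 1 − exp(−*h* × 1) / (1 + *h* × *m*).

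A median of 2 months gives *m* = 2.885 and a median of 6 months gives *m* = 8.656. For *h* = 0.10:

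- 2 months: 1 − 0.9048 / 1.2885 = 29.8%
- 6 months: 1 − 0.9048 / 1.8656 = 51.5%

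| Hazard per month (same for both drugs) | Median 2 months | Median 6 months |
|---|---|---|
| 0.05 | 16.9% | 33.6% |
| 0.10 | 29.8% | 51.5% |
| 0.20 | 48.1% | 70.0% |

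The tail does not create the gap. Without it, incidence is *hm* / (1 + *hm*), which at *h* = 0.10 gives 0.2885 / 1.2885 = 22.4% and 0.8656 / 1.8656 = 46.4%.

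**Step 2: exposure-adjusted incidence.** Under a constant hazard, expected person-time to first event or end of observation equals incidence / *h*. At *h* = 0.10 that is 2.98 months per patient for the first drug and 5.15 for the second. Patients with an event divided by person-time is 0.298 / 2.98 = 0.10 and 0.515 / 5.15 = 0.10. The two drugs now agree, as they should.

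**Step 3: a common 12-week window.** Let *W* = 12 × 7 / 30.4375 = 2.76 months, *w* = *W* − 1 = 1.76 and μ = 1 / *m*. Observation ends at the earlier of 12 weeks and one month after the last dose, so

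incidence = 1 − exp(−*h*) × { [μ / (*h* + μ)] × [1 − exp(−(*h* + μ)*w*)] + exp(−(*h* + μ)*w*) }.

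At *h* = 0.10 this gives 20.5% (median 2 months, μ = 0.3466) and 22.8% (median 6 months, μ = 0.1155). The gap falls from 21.7 to 2.3 percentage points. It does not vanish, because the share with follow-up potentially reaching 12 weeks is exp(−μ*w*): 54% for the first drug and 82% for the second. The window table therefore needs the number at risk beside it.

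**The case against.** **No comparison between drugs is planned.** Objective 2.2.3 is descriptive, 14.3 contains no test between treatments, and 14.1 says of the primary analyses that the aim is not to judge a particular treatment. Incidence by type and grade is also what 5.2.2 literally asks for. This stands, and it limits the harm to how the tables are read. It does not remove the point: 14.3 commits to tables by treatment, and readers will set the columns side by side.

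**The size is hypothetical.** This also stands. The threefold spread in median exposure is assumed. If events cluster soon after the first dose, the gap shrinks. Time on drug is also not truly independent of toxicity, since toxicity is a reason to stop.

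**The wording is open.** That the incidence is crude is inferred from the absence of any other method, and 14.3 speaks of type of treatment rather than agent. The problem exists under either grouping.

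**A stronger reading about visit timing.** A reader might infer that adverse events are looked for only at Cycle 2 Day 1 and then every second cycle, and that drugs with longer cycles would therefore show fewer events. The imaging footnote in 6.0 does imply different cycle lengths: "due to patients on different drug treatment regimen, this may occur at 6 weeks ±2 weeks, 8 weeks ± 2 weeks or 12 weeks ± 2 weeks". The documents do not support that inference:

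- The row "Adverse Event Evaluation" in the schedule is also marked at end of treatment and at safety follow-up.
- Section 6.4 requires at least 30 days of follow-up, by phone if there is no visit.
- Appendix D requires all adverse events that occur to be entered in the trial system.
- Section 9.2 and Appendix D have unexpected grade 4 events, unplanned hospitalisations and deaths reported to the monitoring committee outside the visit schedule.

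A timing bias would need visits to record only what is present that day, and nothing says so. The tables proposed here would not correct visit frequency in any case.

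**Conclusion.** The point holds for exposure. Per-agent incidence as planned in 14.3 combines toxicity with time at risk, and 6.3 makes unequal time at risk likely. Under the stated assumptions, two equally toxic drugs with median times on treatment of 2 and 6 months would differ by about 17 to 22 percentage points in crude incidence, across hazards of 0.05 to 0.20 per month. These figures rest on a constant hazard, exponential time on drug and an invented spread of exposure. They show direction and plausible scale and are not a forecast for this trial.

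The consequence is confined to descriptive safety reporting. No planned test changes, and the primary endpoint is untouched. The documents do not support a further claim of bias from the visit schedule.

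**What to change.** In 14.3, keep the planned tables and add, for each drug or drug class:

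1. the number of patients treated;
2. total person-time from first dose to 30 days after last dose;
3. exposure-adjusted incidence, defined as patients with the event divided by person-time to first event or end of that period;
4. incidence within a common early window from first dose, for example 12 weeks, with the number still at risk.

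**Cost.** SAP wording and two further tables. Section 11.0 already lists a study medication form and an adverse events log, and the registration form records the treatment start date. The sponsor should confirm that these capture last-dose and event-onset dates.

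**Downside.** Rates will be imprecise for drugs given to few patients, which is equally true of the crude tables; grouping by class helps. Exposure-adjusted rates are easiest to interpret when the hazard is roughly constant, which is why the fixed-window table is given as well.

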2.3 Exploratory Objectives

- 2.3.1 To describe health related quality of life in patients undergoing off-label treatment targeting genetic mutations, as measured by the PROMIS-29 Overall Health-Related Quality of Life, Including 4-Item Anxiety Subscale..
- 2.3.2 Using the Satisfaction with Medical Decision Scale, to describe patient satisfaction with decision to pursue off-label treatment.
- 2.3.3 To identify types of actionable mutations with available targeted treatment occurring in cancer patients.
- 2.3.4 To characterize the historical treatment regimens for these patients relative to the targetable mutation.

ClinicalTrials.gov: NCT04111107

- 2.3.5 To describe patient clinical and demographic characteristics of those with actionable mutations based on NGS results.
- 2.3.6 To identify barriers to treatment based on NGS results.

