3.3 Inclusion of Women and Minorities

- 3.3.1 Women and men of all races and ethnicity who meet the above-described eligibility criteria are eligible for this trial.
- 3.3.2 Based on WFBCCC population estimates, we expect approximately 50% of participants to be female, 13% Black or African American, and 6.5% of participants to be of Hispanic ethnicity. 3.0% of the remaining minority population will be comprised of individuals of other ethnicities. Should we not meet or exceed these estimates, the PI will engage the Cancer Center Health Equity Advisory Group to discuss strategies to enhance recruitment in these target populations. However, the population will

ClinicalTrials.gov: NCT04111107

change over time and these estimates may not reflect future ancestral distributions in the future.

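### Section 14.3 fits a logistic model to every mutation type however few its carriers, so models for rare types can have no finite odds ratio

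*Combined protocol and SAP*

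**What the plan says.** Among the exploratory analyses in section 14.3, the combined protocol and SAP states: "Logistic models will be constructed for each type of mutation (yes/no". The stated purpose is "to preliminarily explore associations with clinical and demographic characteristics". The nearest objective, 2.3.5, is descriptive: "To describe patient clinical and demographic characteristics of those with actionable mutations based on NGS results".

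The same section says that "the frequency of types of actionable mutations and previous treatment history will be summarized and demographic characteristics presented". No expected frequency, and no number of mutation types, appears anywhere. For these models, 14.3 gives no minimum number of carriers, no pooling of rare types, no penalised or exact method and no list of covariates.

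The only fallback in 14.3 is general: "Transformations and/or non-parametric approaches will be considered for any outcomes violating parametric assumptions". The only multiplicity adjustment there belongs to the quality-of-life and satisfaction outcomes: "with any between time associations utilizing Tukey adjustment for post-hoc comparisons".

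Section 3.3.2 gives the expected make-up of the sample: "we expect approximately 50% of participants to be female, 13% Black or African American, and 6.5% of participants to be of Hispanic ethnicity". Section 14.4 sets total recruitment at 337.

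**The concern.** The outcome in each model is carrying a given mutation type or not. The information in such a model is limited by the smaller outcome group, which for a rare type is its carriers. If none of the carriers has a trait, the estimated odds ratio for that trait is zero. If all of them have it, the estimate is infinite. In both cases the likelihood keeps rising as the coefficient moves outward. Software then stops at an arbitrary large value with a huge standard error, and the Wald interval built from it has no meaning.

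Two of the demographic traits the plan itself names are uncommon, at 13% and 6.5%, so an empty cell does not need a very small number of carriers. Section 14.3 makes no exception for rare types. Someone following it literally would fit models that cannot be estimated, or would decide after seeing the data which types to drop, pool or treat differently. A transformation or a non-parametric method does not cure separation in a model with a binary outcome.

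What is at stake is the usefulness of one exploratory table.

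**Working it through.** **The plan's own figures.** No figure is stated for the logistic models. The sample size they would draw on does reproduce. A one-sample t-test with difference 0.3, SD 1.71, two-sided 0.05 and 80% power needs 257. Dividing by the Wilcoxon efficiency 3/π gives 257 / 0.955 = 269.1, against the stated 269 evaluable. Then 269 / 0.8 = 336.25, rounded up to 337.

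**Inputs.**
- N = 337 (section 14.4).
- Trait shares q: female 0.50, Black 0.13, Hispanic 0.065 (section 3.3.2).
- Assumed: the share of patients carrying a mutation type, varied from 2% to 20% because the documents give none.
- Assumed: the three traits are independent of each other and of the mutation, and every trait level occurs among non-carriers.

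**One trait, k carriers.** The chance that all carriers fall on the same side of the trait is q^k + (1 − q)^k.

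| Carriers k | Female | Black | Hispanic |
|---|---|---|---|
| 1 | 1.00 | 1.00 | 1.00 |
| 3 | 0.25 | 0.66 | 0.82 |
| 5 | 0.06 | 0.50 | 0.72 |
| 10 | 0.002 | 0.25 | 0.51 |
| 20 | 0.00 | 0.06 | 0.26 |
| 34 | 0.00 | 0.009 | 0.10 |
| 50 | 0.00 | 0.001 | 0.035 |

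For example, with 10 carriers the chance that none is Hispanic is 0.935^10 = 0.51.

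**At least one of the three traits.** For exactly 10 carriers: 1 − (1 − 0.002)(1 − 0.248)(1 − 0.511) = 1 − 0.998 × 0.752 × 0.489 = 0.63.

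Letting the number of carriers vary binomially at N = 337, two simulations of this setting give:

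| Assumed carrier share | Expected carriers | At least one empty cell | At least one non-finite odds ratio |
|---|---|---|---|
| 2% | 6.7 | 78% | 79% |
| 3% | 10.1 | 64% | 64% |
| 5% | 16.9 | 41% | 41% |
| 10% | 33.7 | 12% | 13% |
| 20% | 67.4 | 1% | 1% |

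The third column counts empty cells only. The fourth is a separate simulation of models that have no finite estimate. The two agree to within one percentage point.

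**What a floor of 10 carriers would do.** At N = 337 the chance of fewer than 10 carriers is 0.998 at a 1% share, 0.858 at 2% and 0.025 at 5%. Such a floor would therefore usually remove types carried by about 2% of patients or fewer, and keep those carried by 5% or more. It is not enough alone: with exactly 10 carriers the empty-cell chance is still 0.25 for Black and 0.51 for Hispanic. That is why the floor needs to be paired with a penalised method.

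**The case against.** The strongest reply is that this is unspecified detail in an analysis that the plan itself calls preliminary. The documents say only that the models are logistic. Firth and exact logistic regression are also logistic models, so the wording does not exclude the remedy. Mutation type is not defined: if types are grouped coarsely, by pathway for example, carrier counts rise and the problem nearly vanishes (1% at 67 expected carriers). A failed model is visible when it is run and can be dealt with then.

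Much of this stands. That maximum likelihood would be used is an inference from an unqualified term, and that most types will be rare cannot be shown from the documents. What does not fall away is that 14.3 calls for a model for every type and says nothing about types too rare to model. The preliminary label does not create a finite estimate where there is none, and a rule chosen after seeing the data is weaker than one written beforehand.

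Two stronger readings are tempting and are not supported.

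- *That the models will give infinite odds ratios.* This is a risk that depends on carriers and covariate. For sex alone the chance is about 0.33 at a 1% carrier share and 0.07 at 2%, and a continuous covariate such as age need not separate at all.
- *That the missing multiplicity control is an error.* If 20 independent associations were each tested at 0.05, the chance of at least one false positive would be 1 − 0.95^20 = 0.64. But 14.3 attaches no p-value threshold and no decision to these models. The only 0.05 in section 14 belongs to the primary Wilcoxon test. Nor does the Tukey adjustment elsewhere in 14.3 show an inconsistent policy, since it is the usual companion to pairwise time comparisons after an ANOVA. Leaving labelled exploratory models unadjusted is a matter of how the results are presented.

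**Conclusion.** The concern holds as a minor point about estimation. Followed literally, 14.3 can produce zero or infinite odds ratios with uninterpretable Wald intervals for rare mutation types. On the three shares in 3.3.2 alone, the chance of at least one non-finite odds ratio is about 79% with 7 expected carriers, 64% with 10 and 41% with 17. It drops to 13% with 34 and 1% with 67.

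These figures rest on assumed carrier shares, on independence of the traits, on all 337 patients being in the model, and on the three traits actually being used as covariates, which 14.3 does not confirm. More traits with sparse categories would raise the figures. Coarser mutation groups would lower them. How many types fall in the problem range cannot be told from the documents.

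The primary analysis, the sample size, and the secondary and safety analyses are untouched.

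**What to change.** In section 14.3, state that the mutation-type models will use Firth penalised-likelihood logistic regression and will report odds ratios with profile penalised-likelihood 95% intervals. State that types with fewer than a prespecified number of carriers will be described by counts only. Ten is an example, and any stated number chosen in advance would serve. For the floor to be applied without judgement after the fact, the text should also say what counts as a type and which covariates enter.

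Add a sentence that the results are hypothesis-generating. A false-discovery-rate adjustment may be added but is optional.

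The cost is SAP wording and a different routine in standard software. Odds ratios are shrunk slightly, and rare types are described without being modelled. Near the floor, Firth estimates will be finite but imprecise: 10 carriers imply about 10 × 0.065 = 0.65 expected Hispanic carriers. The profile intervals should show that imprecision.

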At Wake Forest Baptist Comprehensive Cancer Center (“WFBCCC”), solid tumors are most often analyzed using Foundation One CDx, an FDA approved NGS Cancer Profiling Test, while liquid samples are primarily analyzed using an assay from Guardant 360. Other NGS tests employed for tumor analysis include Caris Molecular Intelligence® Comprehensive Tumor Profiling. Results from the testing include any identified ,or actionable, genetic mutations and any known drugs with suspected or proven efficacy for treating these mutations. Off-label drug treatment options are included in the lab report. Additionally, any known drugs that lack efficacy for the tumor are outlined in the report. For many of the identified mutations, however, no off-label drug option is available.

According to WFBCCC data, 9.4% of patients have five or fewer mutations identified in their cancer sample, 48.3% have 10 or fewer, 79.1% have 15 or fewer and 87.9% of patients who have NGS testing exhibit 20 or more genetic mutations in their cancer sample. For many of these mutations, however, no off-label drug is available.

The goal of the current pragmatic trial is to evaluate the impact of a simple method of selecting a treatment approach for identified mutations on subjects' progression free

survival (PFS) by assigning treatment in a balanced manner when no identified optimal off-label treatment is defined. The study also intends to collect information on barriers that providers encounter when prescribing treatment options using the NGS reports and to measure patients' quality of life before, after, and during treatment.

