6.3 Duration of Therapy

In the absence of treatment delays due to adverse events, treatment may continue for the number of cycles indicated on the FDA label, or until one of the following criteria applies:

- Disease progression,
- Intercurrent illness that prevents further administration of treatment,
- Unacceptable adverse event(s),
- Patient decides to withdraw from the study, or

- General or specific changes in the patient's condition render the patient unacceptable for further treatment in the judgment of the investigator.

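### After Cycle 2 Day 1, quality of life is scored only at End of Treatment, an event-driven visit that the planned repeated measures ANOVA treats as a common time point

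*Combined protocol and SAP*

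**What the plan says.** Section 14.3 gives the analysis for both patient-reported scales: "For quality of life and patient satisfaction outcomes, changes over time will be assessed using a repeated measures ANOVA". Pairwise comparisons of visits are to be Tukey-adjusted. The section does not define the levels of time. These have to be read from the Study-Related Activities table in section 6.0.

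In that table PROMIS-29 and the "Satisfaction with Medical Decision Scale" are each marked in three columns: Pre-Study, Cycle 2 Day 1 and "End of Treatment ±7 days". Both rows are blank in the column for Day 1 of later even cycles and in the safety follow-up column. The even-cycle column does carry physical examination, performance status, blood tests, imaging and adverse event evaluation.

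Section 6.3 determines when End of Treatment falls: "treatment may continue for the number of cycles indicated on the FDA label, or until one of the following criteria applies". The criteria that follow are progression, another illness, intolerable adverse events, patient withdrawal, and a change in condition that the investigator judges to rule out further treatment.

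Section 1.0 says the study will measure "quality of life before, after, and during treatment". Objective 2.3.1 is exploratory and descriptive, and concerns patients undergoing off-label treatment.

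**The concern.** A repeated measures ANOVA with Tukey comparisons takes each visit as a level of a common time factor. Pre-Study and Cycle 2 Day 1 fit that description, apart from differences in cycle length between drugs. End of Treatment does not. It is an event, reached after a few weeks by one patient and after a year by another, and for different reasons.

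The third level of time therefore pools unlike things. A difference between it and an earlier visit may reflect elapsed time, the circumstances of stopping, or the mix of stop reasons in the sample, and the planned analysis has no means of separating them. Patients with the longest treatment, who matter most to a study of whether the selection approach helps, contribute no score between the start of their second cycle and the point at which they stop. Objective 2.3.1 asks about life on treatment, and beyond the first cycle the data would not show it.

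The issue is when scores are taken. It is separate from how missing questionnaires are handled.

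**Working it through.** The plan states no figure for quality of life. The sample size in section 14.4 is for the PFS ratio and has no bearing here. The check is a reading of the schedule plus three pieces of arithmetic. Every input not in the documents is marked as an assumption.

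**1. Scores available per patient.** From the section 6.0 table there is one before treatment, one on treatment (Cycle 2 Day 1) and one at End of Treatment. The three pairwise contrasts are:
- Baseline versus Cycle 2 Day 1: both visits are scheduled and neither is triggered by stopping. This contrast is valid.
- Baseline versus End of Treatment, and Cycle 2 Day 1 versus End of Treatment: both involve the event-driven visit.

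The allowance in section 14.3 for transformations or non-parametric methods addresses the distribution of the scores, not the timing.

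**2. Length of the gap.** Assumption: cycles of 3 or 4 weeks, since length varies by drug. Cycle 2 Day 1 then falls at week 3 or 4, and the gap is time on treatment minus 3 or 4. Day 1 of even cycle c falls at week (c − 1) × cycle length, and visits before the stop are counted from cycle 4.

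| Weeks on treatment | Cycle length | Gap without a score | Even-cycle visits without PROMIS-29 |
|---|---|---|---|
| 24 | 3 weeks | 24 − 3 = 21 weeks | 3 (weeks 9, 15, 21) |
| 24 | 4 weeks | 24 − 4 = 20 weeks | 2 (weeks 12, 20) |
| 52 | 3 weeks | 52 − 3 = 49 weeks | 8 (weeks 9 to 51, every 6) |
| 52 | 4 weeks | 52 − 4 = 48 weeks | 5 (weeks 12 to 44, every 8) |

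**3. Spread of the End of Treatment visit.** Assumption: time on treatment is exponential with median 16 weeks. The 10th percentile is 16 × ln(1/0.9)/ln 2 = 2.4 weeks, and the 90th is 16 × ln(10)/ln 2 = 53 weeks. All of these would enter the ANOVA as one time point.

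**4. What the End of Treatment contrast measures.** Assumptions: the score changes by b points from baseline while on treatment. A failure-type stop puts it 5 points below baseline whatever b was. Any other stop leaves it at b. With p the share of failure-type stops, the mean change from baseline to End of Treatment is p × (−5) + (1 − p) × b.

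| b | p = 1.0 | p = 0.8 | p = 0.5 |
|---|---|---|---|
| 0 | −5.0 | −4.0 | −2.5 |
| +3 | −5.0 | −3.4 | −1.0 |
| +5 | −5.0 | −3.0 | 0.0 |

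For example, with b = +3 and p = 0.8: 0.8 × (−5) + 0.2 × 3 = −3.4. The 5-point fall is an input, so the table is not evidence that scores will fall. It shows that, if stopping does affect the score, the contrast depends on the mix of stop reasons. At p = 1.0 it carries no information about b. If stopping had no effect, the contrast would equal b for every p and there would be no distortion.

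**5. Whether analysis alone can repair it.** On the present schedule every score after Cycle 2 Day 1 is an End of Treatment score. Replacing visit by weeks since first dose leaves later time fully confounded with stopping. For patients who reach Cycle 2 Day 1, change from the last on-treatment score is simply End of Treatment minus Cycle 2 Day 1, which the Tukey comparisons already provide.

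**The case against.** The strongest defence is that the three assessments deliver what section 1.0 promises: one score before, one during and one at the end. No document promises a trajectory. The objective is exploratory, the trial is pragmatic, and patients with ECOG up to 3 should not be burdened lightly. This stands as a reason for low severity. It does not answer the point that section 14.3 reads an event as a time.

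A reader might infer that the analysis merely compares baseline with the moment of treatment failure. The documents do not support that. The baseline versus Cycle 2 Day 1 contrast is available, and section 6.3 also allows treatment to end through completed label cycles, withdrawal or toxicity. That most stops will be for progression is plausible in this population, but no section gives the shares.

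A reader might also infer that a decline is bound to be reported. That follows only from an assumed fall around stopping. Baseline is itself often close to progression: a footnote to the schedule expects imaging showing progression within 60 days of registration. The direction of the contrast is therefore open.

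Finally, scores at even cycles would come only from patients still on treatment. That stands, and the analysis must say so.

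**Conclusion.** The concern holds in a limited form. Change in quality of life after Cycle 2 Day 1 is observed only at End of Treatment, whose timing and meaning depend on why the patient stopped, and section 14.3 does not allow for this. The later time effect cannot be separated from the effect and mix of stop reasons. The early on-treatment contrast is unaffected.

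The schedule marks and the list of stop reasons come straight from the documents. The gaps of 20 to 21 and 48 to 49 weeks rest on assumed cycle lengths. The spread of the visit and the contrasts between −5 and 0 points are illustrations on assumed values. The documents do not give the direction or size of any real distortion. No primary, secondary or safety conclusion is affected, so this is a cheap improvement to an exploratory objective.

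**What to change.** 1. **Schedule, section 6.0.** Mark PROMIS-29 in the existing column for Day 1 of even cycles after Cycle 2.
2. **Section 14.3, on-treatment scores.** Model them against weeks since first dose with a mixed model that uses actual assessment dates. State that later scores describe patients still on treatment.
3. **Section 14.3, End of Treatment.** Take it out of the common time factor. Report it as change from the last on-treatment score (from Pre-Study for patients who stop before Cycle 2 Day 1), with the distribution of its timing and by reason for stopping. The satisfaction scale has the same three marks and should have its End of Treatment score reported by timing and stop reason too.

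If no forms are added, a change to section 14.3 only allows End of Treatment to be reported as an event, by timing and stop reason. It does not recover on-treatment change, and the text should not suggest that it does.

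The cost is one more short questionnaire at visits already scheduled: on the cycle lengths assumed above, 2 to 3 extra forms for a patient treated 24 weeks and 5 to 8 for one treated 52 weeks. There is also some data entry and a few sentences in section 14.3. Scores not collected during treatment cannot be recovered later.
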